#### 4.1.1. Dose Escalation

Dose escalation of LY3475070 will be driven by the modified toxicity probability interval-2 (mTPI-2) method (Guo et al. 2017) where a pre-calculated decision table (Appendix 8) will guide the dose recommendations until the MTD is determined (e.g., when all planned patients have been tested, or when no higher candidate DL can be tested). Dose escalation decision will also take into consideration available PK and pharmacodynamic data from previous DLs. Although mTPI-2 allows flexible number of patients in each dosing cohort, a minimum of 3 evaluable patients are required for the DLT evaluation at each DL. The first patient of each DL (in Phase 1a) will be observed for 48 hours before additional patients are enrolled to that DL. Inpatient dose escalation is not allowed.

Like the 3+3 design, the mTPI-2 method incorporates prespecified escalation rules. In contrast, the mTPI-2 method is based on quantitative models that incorporate uncertainty into the decision rules, thereby allowing more precise RP2D selection. If 3 or 6 patients are enrolled in a cohort, the escalation rule parallels a traditional 3+3 design. However, it allows flexible number of patients in a cohort. For example, with 2 DLTs per 6 patients enrolled, the mTPI-2 would recommend staying at the current dose, as analogy to 1 DLT per 3 patients enrolled in 3+3 design; therefore, it allows more patients for a more precise estimate of the DLT rate at this DL.

Following a discussion between the Lilly CRP/CRS and the investigators, a more conservative dose selection may be applied to the next cohort (for instance, if PK/pharmacodynamics data suggest that further dose increase would not be expected to yield additional benefit). For

example, if the rule indicates “E” to escalate, the dose may stay at the current DL, be de-escalated to a lower level, or escalation may cease. In the mTPI-2, the cohort size is not fixed. However, each DL in this study will be tested with a minimum of 3 evaluable patients, unless the escalation rules dictate that the dose should be de-escalated (“D” or “DU”). Doses can be escalated, de-escalated, and re-escalated. If the dose decision was “DU,” the dose cannot be re-escalated to that level.

This study is designed to identify a DL with a dose-limiting target toxicity rate of 30%. The mTPI-2 method considers an equivalence interval (EI) around the target toxicity rate. For this study, the EI is elicited to be (25%, 35%), resulting in the rules below.

Safety data, in particular DLTs, will be the primary criteria for the dose escalation. In addition, if available at the time of dose escalation decision, PK/pharmacodynamics results (for example,  $C_{max}$ , area under the concentration curve (AUC), pharmacodynamics results) will be used as secondary/supporting data for dose escalation.

Intermediate and/or higher dose as well as alternative schedules of administration will be explored if deemed necessary after discussion between Lilly and investigators and taking into account patient safety and PK/pharmacodynamics data. If needed, additional patients may be enrolled to further assess PK/pharmacodynamics or tolerability.

In order to be DLT-evaluable, patients must have received 75% of LY3475070 scheduled dose within the 28-day DLT period unless patients have a DLT qualifying event. For patients treated with the combination treatment, patients must have received 75% of LY3475070 and a minimum of 1 pembrolizumab infusion within the 28-day DLT period.

In the dose escalation phase, once a given DL is cleared for DLT evaluation and is deemed safe, the dose cohort may be expanded to further investigate the safety, PK, pharmacodynamic, and clinical activity of LY3475070 and the combination with pembrolizumab. There will be up to 20 backfill patients enrolled across all dose levels in cohorts A and B combined in the phase 1a study. Any AEs reported by those backfilled patients that meet the DLT criteria as defined in Section 6.1.1.1 and occur in the DLT period are considered DLT-equivalent toxicities (Section 6.1.1.2). The cumulative safety data from the cohorts previously declared safe and the current dose cohort under evaluation will be continuously monitored. A Bayesian toxicity monitoring rule will be implemented for DLT-equivalent toxicities added from backfill patients (Section 9.2). These aggregate safety data will be included in defining the RP2D.

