## 4. Study Design

### 4.1. Overall Design

Study JZMA is an open-label, multicenter, global, 2-part Phase 1 study of LY3475070 alone or in combination with pembrolizumab in advanced cancer patients.

Phase 1a of the study will target the following tumor types: triple negative breast cancer, pancreatic cancer, PD-1 refractory NSCLC, PD-1 refractory RCC, PD-1 refractory melanoma, metastatic castrate resistant prostate cancer (mCRPC) and ovarian cancer. In **Cohort A** in Phase 1a, escalating doses of single agent LY3475070 will be evaluated in at least 3 evaluable patients per dose level (i.e., DLA1-A4, see Schema in Section 1.2). However, based on the observed PK, pharmacodynamic, and safety data observed, not all provisional dose levels may be explored. Intermediate and/or higher dose as well as alternative schedules of administration (BID dosing) will be explored if deemed necessary after discussion between Lilly and investigators. The dose limiting toxicity (DLT) observation period will be 28 days. The first patient of each DL will be observed for 48 hours before additional patients are enrolled to that DL. The totality of safety data will be reviewed by the Lilly clinical research physician/clinical research scientist (CRP/CRS) and study investigators prior to escalating to a next DL. Inpatient dose escalation is not allowed. In the dose escalation phase, once a given DL is cleared for DLT evaluation and is deemed safe, the dose cohort may be expanded (i.e., backfilled) to a maximum of 20 patients to further investigate the safety, PK, pharmacodynamic, and clinical activity. Enrollment of patients to the dose cohort for DLT evaluation/dose escalation will take precedent. To ensure that patients are not unnecessarily enrolled to subtherapeutic dose levels, these backfills will not be undertaken until a DL already declared safe also demonstrates evidence of therapeutic exposures. However, continuous safety monitoring (Section 9.2) will be implemented to ensure ongoing evaluation of patient safety in backfill patients. In the event that backfill enrollment/escalation is paused, the aggregated safety data will be evaluated to determine if the dose level in question (and higher dose levels) should be permanently discontinued. In general, all available toxicity and PK data will be utilized, including DLT equivalents observed from backfill patients, to recommend an escalation/de-escalation decision, and to inform the selection of the RP2D.

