### 6.1.1. Definition of DLT and DLT-ET

#### 6.1.1.1. DLT

A DLT is defined as any of the events listed in the table below, if both of the following criteria are met:

- the event occurs during the DLT observation period (28 days) in Phase 1a, and
- the event cannot, in the opinion of the investigator, be definitely attributed to primary disease or extraneous causes, such as accident.

Patients who experience a DLT in the DLT observation period will be discontinued from study treatment.

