**6.1.1.2. DLT-ET**

A **DLT-equivalent toxicity (ET)** is any event listed in Section 6.1.1.1 occurring after the DLT observation period in Phase 1a or any cycle in Phase 1b.

A DLT-ET is an AE that meets the DLT criteria as defined above and occurs in any cycle other than the DLT assessment period (28 days for Cohorts A1 through A4 and B1 through B3). In addition to the DLT assessment period, available safety data beyond the DLT assessment period may also be taken into consideration prior to a decision to advance to the next DL or the determination of the RP2D.

Potential DLTs that are AEs, which are reasonably anticipated AEs for concomitant medication should be reviewed by the treating investigator and Lilly CRP/CRS before final determination as a DLT. Review and discussion may include additional participating investigators. Such review

may determine that confounding factors render the case to be not evaluable for the purposes of dose selection.

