#### Estimated Incidence Rate and 2-Sided 95% CI

N=20				N=40			
Number of Cases	Estimated Rate	95% CI a		Number of Cases	Estimated Rate	95% CI a	
		Lower Limit	Upper Limit			Lower Limit	Upper Limit
0	0.0	0.0	0.17	0	0.0	0.0	0.09
3	0.15	0.03	0.38	5	0.12	0.04	0.27
5	0.25	0.09	0.49	10	0.25	0.13	0.41
10	0.50	0.27	0.73	15	0.38	0.23	0.54
15	0.75	0.51	0.91	20	0.50	0.34	0.66

Abbreviations: CI = confidence interval; N = number of patients.

a 95% Clopper-Pearson interval for binomial distribution.

In the dose escalation phase, once a given DL is cleared for DLT evaluation and is deemed safe, the dose cohort may be expanded with backfill patients to further investigate the safety, PK, pharmacodynamic, and clinical activity of LY3475070 and the combination with

pembrolizumab. There will be up to 20 backfill patients enrolled across all DLs in Cohorts A and B combined in the phase 1a study. Enrollment of patients to the dose cohort for DLT evaluation/dose escalation decision will take precedent. A Bayesian toxicity monitoring rule will be implemented to ensure continuous safety monitoring, assuming DLT or DLT-equivalent events arise from a beta-binomial model. Specifically, if the  $Prob(\text{true DLT or DLT-equivalent rate} > 35\%) > 55\%$  in any given cohort, the enrollment to that cohort will be halted. A 35% rate is targeted to be consistent with the mTPI-2 equivalence interval upper bound. A Beta(1, 1) prior for the true rate is utilized. The stopping boundaries for this safety monitoring rule based on the aggregated data is listed in the following table.

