### Bayesian Toxicity Monitoring Rules

Number of Patients	Pause if Number of Patients with DLT or DLT Equivalent
4-5	$\geq 2$
6-8	$\geq 3$
9-11	$\geq 4$
12-14	$\geq 5$
15-16	$\geq 6$
17-19	$\geq 7$
20	stop

Abbreviations: DLT = dose-limiting toxicity.

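### The Protocol gives two opposite time windows for a backfill patient's DLT-equivalent, so the Section 9.2 pause rule does not say whether events from Day 29 count

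*Protocol*

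**What the plan says.** Protocol Section 6.1.1.1 limits a DLT in time: "the event occurs during the DLT observation period (28 days) in Phase 1a".

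Protocol Section 4.1.1 covers backfill patients. Their adverse events that "meet the DLT criteria as defined in Section 6.1.1.1 and occur in the DLT period are considered DLT-equivalent toxicities" are to be handled under Section 6.1.1.2, and the same paragraph sends them to the Bayesian rule in Section 9.2.

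Protocol Section 6.1.1.2 says that a DLT-equivalent "is any event listed in Section 6.1.1.1 occurring after the DLT observation period in Phase 1a or any cycle in Phase 1b". It then restates this: "A DLT-ET is an AE that meets the DLT criteria as defined above and occurs in any cycle other than the DLT assessment period", and gives that period as 28 days for the Cohort A and B dose levels. It sets no upper time limit.

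Protocol Section 9.2 halts enrolment to a cohort when the posterior probability that the true rate exceeds 35% is above 55%, under a Beta(1,1) prior. On the limit it says: "A 35% rate is targeted to be consistent with the mTPI-2 equivalence interval upper bound". The boundary table is headed "Pause if Number of Patients with DLT or DLT Equivalent" and is applied to aggregated data. Neither the text nor the table gives a time window.

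On what follows a pause, Protocol Section 4.1 says: "In the event that backfill enrollment/escalation is paused, the aggregated safety data will be evaluated". The review decides whether the dose level is permanently dropped.

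**The concern.** Backfill patients belong to Phase 1a, so the Phase 1b part of Section 6.1.1.2 does not apply to them. For these patients the two definitions exclude each other: one requires the event to fall inside the 28 days, the other outside. A reader who follows the citation in Section 4.1.1 arrives at the opposite rule.

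Section 9.2 does not settle the matter, because it pools escalation and backfill patients. The backfill sentence in Section 4.1.1 does not reach the escalation patients. For them, a DLT-equivalent under Section 6.1.1.2 can only be an event from Day 29 onward. A reader could therefore apply the 28-day window to backfill patients and still have textual grounds to count late events in escalation patients.

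This is the numeric safety rule for up to 20 backfill patients in a study without a data monitoring committee, and it should give one answer from one dataset. Late events are plausible: Section 6.6.2 notes that immune-related events can appear months after dosing, and such events of Grade 3 or higher are DLT criteria. An open-ended count would also depend on follow-up time and accrual speed as well as on the toxicity of the dose.

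**Working it through.** **1. Reproduce the boundary table.** Inputs from Section 9.2: Beta(1,1) prior, 35% rate limit, 55% probability cut-off. With y patients with events among n, the posterior is Beta(1+y, 1+n−y). The boundary is the smallest y for which P(p > 0.35) > 0.55. For n = 4 to 19 this gives 2 (n = 4-5), 3 (6-8), 4 (9-11), 5 (12-14), 6 (15-16) and 7 (17-19), as printed. The closest case is 6 of 17, where P = 0.549 falls just short. The table is correct; only the event that feeds it is unclear.

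**2. Which events are in doubt.**

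| Event in a backfill patient meeting the 6.1.1.1 criteria | 4.1.1 | 6.1.1.2 | Counted under 9.2? |
|---|---|---|---|
| Days 1-28 | DLT-equivalent | not a DLT-equivalent, but a DLT under 6.1.1.1 | yes, on either reading |
| Day 29 onward | not a DLT-equivalent | DLT-equivalent, no end date | depends on the reading |

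**3. Can one late event change the action?** This needs no assumed rate. Take n = 10, with 3 patients having an event in Days 1-28:
- 28-day count, y = 3: posterior Beta(4, 8), P(p > 0.35) = 0.426. Continue.
- One further patient with an event after Day 28, counted, y = 4: posterior Beta(5, 7), P = 0.668. Pause.

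**4. How often might it matter? An illustration under assumed inputs.** The documents give neither a DLT rate nor a late-event rate. Assumptions:
- true 28-day rate 15%, so the cumulative hazard over 28 days is L = −ln(0.85) = 0.1625;
- late hazard r times the 28-day hazard, with r from 1/10 to 1/3;
- every patient followed for 9 or 12 weeks, so k = (63−28)/28 = 1.25 or (84−28)/28 = 2;
- the level was cleared at 0 of 3, and the boundary is checked after each added patient up to n = 19.

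Backfill patient, any event by end of follow-up: 1 − exp(−L(1 + rk)), which is 16.7-20.6% at 9 weeks and 17.7-23.7% at 12 weeks. Escalation patient still event-free at Day 28, later event: 1 − exp(−Lrk), which is 2.0-6.6% and 3.2-10.3%. Exact recursion then gives the probability of a pause by 19 patients:

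| Events counted | 9 weeks | 12 weeks |
|---|---|---|
| Days 1-28 only | 5.6% | 5.6% |
| plus late events in backfill patients | 7.5-13.2% | 8.8-19.3% |
| plus late events in escalation patients too | 9.4-20.4% | 12.0-31.1% |

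Reaching n = 19 from 3 patients would use 16 of the 20 backfill places shared across Cohorts A and B.

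**The case against.** The strongest reply is that the text already leans one way. Section 4.1.1 is the provision written for backfill patients, and it defines their DLT-equivalents and names the Section 9.2 rule in the same paragraph. The 35% limit is tied to the mTPI-2 interval, which concerns 28-day DLTs. The amendment history lists a clarification of the DLT-equivalent definition under Amendment (a), while the backfill language came in with the current amendment, so the defect looks like an unrevised cross-reference. This stands as evidence of intent. It does not remove the conflict, because Section 9.2 pools both groups of patients and states no window.

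A second reply is that the consequence is small: counting late events errs toward caution, a pause brings a review, and events after Day 28 already reach the safety and RP2D review through Sections 4.1, 6.1.1.2 and 6.1.2. That also stands.

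A third reply is that the pause probabilities rest on invented inputs and shrink when only backfill patients contribute late events. That is correct, and is why both versions are shown.

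A reader might also infer that the same unclear count drives dose escalation, because Section 4.1 brings in safety data "including DLT equivalents observed from backfill patients, to recommend an escalation/de-escalation decision". The documents do not support this. That sentence describes the use of all available toxicity and PK data, Section 6.1.1.2 expressly allows data from beyond the DLT period to be considered, and the numeric escalation table in Appendix 8 counts DLTs.

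**Conclusion.** The conflict is real and lies in the current Protocol text: Sections 4.1.1 and 6.1.1.2 give opposite windows, and Section 9.2 does not choose between them. It is confined to events from Day 29. The 28-day reading is the likelier intention, but two careful readers could reach different pause decisions from the same data. That one late event can change the action rests on no assumption. How often it would do so is unknown; the ranges above depend on the assumed 15% rate, late hazard and follow-up, and should be read as illustration only.

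A reader might infer that early toxicity in backfill patients escapes the rule, or that the ambiguity could cost a dose level automatically. Neither follows: events in Days 1-28 count on either reading, and a pause leads to an evaluation of aggregate safety data. Nor is a stricter cumulative rule wrong in itself, provided its window is stated. This is a minor wording correction to a numeric safety rule.

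**What to change.** - **Protocol 9.2:** state that the rule counts escalation and backfill patients at the dose level who have an event meeting the 6.1.1.1 criteria in Days 1-28.
- **Protocol 6.1.1.2:** add the backfill definition, so that the cross-reference from 4.1.1 agrees with it.
- **Events from Day 29:** keep them in the cumulative safety and RP2D review already provided in 4.1, 6.1.1.2 and 6.1.2.
- **Alternative:** if the sponsor wants late events in the numeric rule, state that window explicitly in 9.2 instead.

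The cost is a few sentences; the boundary table does not change. Under the 28-day option, late toxicity is handled by review and not by a numeric limit.

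Separate and minor: SAP 6.9.2 summarises Phase 1a DLT-equivalents only after Cycle 2. Events from Day 29 to the end of Cycle 2 (Day 42 on the Protocol's 21-day cycle, Day 56 on the 28-day cycle in SAP 6.9.1) would then appear in neither the DLT nor the DLT-equivalent summary, though still in the general adverse event tables. The SAP was written for Protocol (a) and has no backfill rule, so it has no bearing on the pause decision. When it is updated, the wording should become after Day 28.

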#### **4.1.2. In Vitro Diagnostic Utilization**

An investigational CD73 IHC assay will be utilized to determine CD73 protein expression status in patients that otherwise meet all other eligibility criteria for enrollment in Phase 1b Cohort C. The test will be performed at a central laboratory following routine processing for histological evaluation using a commercial autostainer platform and will be interpreted by qualified pathologists. Patients will be required to undergo a mandatory fresh biopsy of a primary or metastatic site to obtain tumor tissue for determining CD73 expression. Patients that are not positive for CD73 expression, despite meeting all other eligibility criteria, will be screen failures.

In an initial survey of CCI formalin-fixed paraffin-embedded (FFPE) tumor samples conducted with an investigational IHC assay, CD73 expression was observed in CCI of lung tumors CCI. Recently disclosed external studies, using IHC-based assessment of CD73 expression,

have reported an overall prevalence of CD73 in RCC of 22% (25/112 [Tripathi et al. 2019]). Tumor cell CD73 expression has been detected in 54% (62/114) of metastatic melanoma (Monteiro et al. 2018), and in 73% and 40% of adenocarcinoma and squamous cell carcinoma of the lung respectively (Salazar et al. 2018).

## **4.2. Scientific Rationale for Study Design**

Multiple tumor types have shown CD73 expression to have a prognostic value (Allard et al. 2019), including tumors insensitive to PD-1/L1 or CTLA-4 checkpoint blockade such as TNBC (Loi et al. 2013) and mCRPC (Leclerc et al. 2015). In preclinical models of such “immune cold” tumors, combined treatment targeting CD73 and checkpoints CTLA4 or PD-1/L1 showed synergy in comparison to single agent treatment (Allard et al. 2012). Several agents targeting A2AR and CD73 have recently entered the clinic and are being evaluated in patients with solid tumors (Leone and Emens 2018). Responses have been noted either as single agent treatment, or in combination with PD-1/L1 targeting antibodies, including in immune “cold” tumors not sensitive to ICI such as mCRPC, ovarian and pancreatic cancer (Sui et al. 2018; Bendell et al. 2019). In addition, translational data from the ongoing Phase 1/2 study with CPI-444, an antagonist of A2AR, has suggested that patients with higher tumoral expression of CD73 and A2AR benefit from treatment (Hotson et al. 2017). Interestingly, patients that had been on a PD-1/L1 for a prolonged duration prior to study entry had elevated A2AR and CD73 expression suggesting the adenosine pathway may play a role in acquired resistance to PD-1/L1 treatment. Additional work on patient samples from this study also revealed patients that had a high intratumoral activation of the adenosine pathway to benefit from study treatment in comparison to patients with a low activation signature (Willingham et al. 2018).

Study JZMA will evaluate the safety and efficacy of LY3475070 either as single agent or in combination with pembrolizumab in tumors known to be immune “cold” such as mCRPC, as well as immune “inflamed” tumors that are unresponsive to check point inhibition, as a consequence of an immune suppressive TME infiltrated by myeloid and other immune regulatory cells. The underlying clinical hypothesis is that targeting CD73 within the TME will reduce local adenosine levels, an important immune-suppressive metabolite. This can be expected to reduce the inhibitory signals of immune suppressive cells, which may lead to increased T-cell infiltration and activation within the TME and lead to improved clinical responses.

Owing to the primary focus on patient safety in early clinical development an open label study is appropriate and an mTPI-2 based dose escalation is an appropriate design feature as it allows for more comprehensive and nuanced decision making in Phase 1a of this study. In Phase 1b, randomization of patients to monotherapy or combination therapy in 2 of 3 cohorts is an appropriate means of ensuring balanced patient characteristics in both treatment arms.

## **4.3. Justification for Dose**

### **4.3.1. LY3475070**

A clinical starting dose of 150 mg QD of LY3475070 administered orally in humans is anticipated to be safe and have the potential for clinical efficacy. Based on predicted human pharmacokinetics and a PK/pharmacodynamic model established on the basis of

pharmacodynamic data CCI

a dose of 150 mg QD is anticipated to result in an average target inhibition of CCI over the dosing interval and CCI at  $C_{min}$  (refer to Section 4.2.3 of the IB for details). Target inhibition of this magnitude is expected to result in clinically meaningful reduction of adenosine formation by CD73. Margin of Safety for oral administration of LY3475070 based on administered dose and predicted exposure is presented below.

